### **Exclusion criteria for prior or current systemic medication**

20. Use of other investigational drugs within 30 days or 5 half-lives of Baseline (Day 1), whichever is longer.
21. Use of any systemic anti-VEGF drugs within 6 months before Baseline (Day 1) (e.g., sorafenib (Nexavar®), sunitinib (Sutent®), bevacizumab (Avastin®), ziv-aflibercept (ZALTRAP®)).
22. Current or planned use of systemic medications known to be toxic to the lens, retina or optic nerve, including deferoxamine, chloroquine/hydroxychloroquine (Plaquenil®),

tamoxifen, phenothiazines other than temporary use with common cold and upper respiratory infection (i.e. exclude PL granules), and ethambutol.

## **Exclusion criteria for prior or current ocular treatment**

### **For both eyes**

23. Treatment (or anticipated treatment in the fellow eye for non-RVO indications during the study) with any anti-angiogenic drugs (including any anti-VEGF agents) within 3 months before Baseline (Day1) in fellow eye or before Baseline (Day 1) in the study eye (e.g., pegaptanib (Macugen®), ranibizumab (Lucentis®), bevacizumab (Avastin®), and aflibercept (EYLEA®)).

### **For study eye**

24. Panretinal laser photocoagulation within 1 month before Baseline (Day1) or anticipated or scheduled within the next 12 months (Study periods) following Baseline (Day1).
25. Any giving of focal or grid laser photocoagulation before Baseline (Day1).
26. Any intraocular procedure (including Yttrium-Aluminum-Garnet capsulotomy) within 2 months before Baseline (Day1) or anticipated within the next 12 months following Baseline (Day1).
27. Topical ocular or systemic corticosteroids administered for at least 30 consecutive days within 6 months before Screening.
28. Use of intra- or periocular corticosteroids (including sub-Tenon) within 3 months before Screening.
29. Any use of intraocular corticosteroid implants (e.g., dexamethasone (Ozurdex®), fluocinolone acetonide (Iluvien®)).
30. History of optic neurotomy, sheathotomy, or filtration surgery at any time.
31. Macular BRVO ([Battaglia Parodi et al. 1999](#)).

No additional exclusions may be applied by the investigator, in order to ensure that the study population will be representative of all eligible patients.

## **5 Treatment**

### **5.1 Study treatment**

#### **5.1.1 Investigational and control drugs**

The investigational treatment used in this study is 0.5 mg ranibizumab applied PRN as intravitreal injection of 0.05 mL, with or without the laser treatment. Commercially available ranibizumab prefilled syringes (PFS) for injection will be supplied (open label) to each study center by Novartis Pharma K.K. for the treatment of study eye. Novartis Pharma K.K. will not be providing/supporting ranibizumab for the treatment of fellow eye however investigator can treat visual impairment of fellow eye due to ME secondary to RVO using ranibizumab purchased by patient. Each PFS contains ranibizumab in the concentration of 10 mg/mL. PFSs of ranibizumab are for single use only and the content of the PFS must not be split.

**Arm 1:** Patients with visual impairment due to ME secondary to BRVO are treated with ranibizumab monotherapy with an individualized stabilization-criteria-driven PRN dosing regimen as described in [Section 5.5.4.1](#) and [Section 5.5.4.2](#).

**Arm 2:** Patients with visual impairment due to ME secondary to BRVO are treated with ranibizumab with an individualized stabilization-criteria-driven PRN dosing regimen. The laser photocoagulation is applied as described in [Section 5.5.4.1](#) and [Section 5.5.4.2](#).

### **5.1.2 Additional treatment**

No additional treatment beyond investigational drug and control drug are included in this trial.

## **5.2 Treatment arms**

Patients will be assigned to one of the following 2 treatment arms in a ratio of 1:1.

Arm 1: ranibizumab monotherapy

Arm 2: ranibizumab with Grid&Direct short pulse laser photocoagulation combination therapy

## **5.3 Treatment assignment and randomization**

At Baseline (Day1) all eligible patients will be randomized via Interactive Response Technology (IRT) to one of the treatment arms. The investigator or his/her delegate will contact the IRT after confirming that the patient fulfills all the inclusion/exclusion criteria. The IRT will assign a randomization number to the patient, which will be used to link the patient to a treatment arm.

The randomization numbers will be generated using the following procedure to ensure that treatment assignment is unbiased and concealed from patients/subjects and investigator staff. A patient randomization list will be produced by the IRT provider using a validated system that automates the random assignment of patient numbers to randomization numbers. These randomization numbers are linked to the different treatment arms.

The randomization will be balanced by VA ( $0.3 <$ , or  $\geq 0.3$  assessed by decimal VA which is translated into 58 letters in EDTRS).

The randomization scheme for patients will be reviewed and approved by a member of the Biostatistics Quality Assurance (BQA) Group.

## **5.4 Treatment blinding**

This is an open-label study; therefore treatment blinding (masking) is not applicable. However, masking of the Vision Examiner, assessing parameters constituting the secondary endpoint (BCVA), will be chosen at each site before the study start. Therefore, the Vision Examiner will not be allowed to access unmasked medical records and to perform any other tasks involving direct patient care which may unmask him/her to the patient's treatment.

## **5.5 Treating the patient**

Sponsor qualified medical personnel will be readily available to advise on trial related medical questions or problems.

### **5.5.1 Patient numbering**

Each patient is uniquely identified in the study by a combination of his/her center number and patient number. The center number is assigned by Novartis to the investigative site. Upon signing the informed consent form, the patient is assigned a patient number by the investigator. At each site, the first patient is assigned patient number 1, and subsequent patients are assigned consecutive numbers (e.g. the second patient is assigned patient number 2, the third patient is assigned patient number 3). The investigator or his/her staff will contact the IRT and provide the requested identifying information for the patient to register them into the IRT. For studies using electronic Case Report Forms (eCRFs), only the assigned patient number must be entered in the field labeled "Patient ID" on the electronic data capture (EDC) data entry screen (e.g. enter '1', '2', etc.). Once assigned to a patient, the patient number will not be reused. If the patient fails to be randomized for any reason, the IRT must be notified within 2 days that the patient was not randomized. The reason for not being randomized will be entered on the Screening Log, and the Demography eCRF should also be completed.

### **5.5.2 Dispensing the study drug**

Each study site will be supplied with investigational drug in packaging.

Immediately before dispensing and administering the investigational drug, Investigator staff will write the drug name, strength, Packaging lot number and expiry date from the label onto the source document (and/or Drug Accountability Log) containing that patient's unique patient number. Site may apply an additional label/sticker on the drug kit containing the following information for accountability purpose: Study number, Study name.

### **5.5.3 Handling of study and additional treatment**

#### **5.5.3.1 Handling of study treatment**

Study treatment will be supplied by Novartis at the study site and must be received by a designated person, handled and stored safely and properly, and kept in a secured location to which only the investigator and designees have access. Upon receipt, all study treatment must be stored according to the instructions specified on the labels. Clinical supplies are to be dispensed only in accordance with the protocol. Technical complaints are to be reported to the respective Novartis CPO Quality Assurance.

Medication labels will be in the local language and comply with the legal requirements of Japan.

The investigator must maintain an accurate record of the shipment and dispensing of study treatment in a drug accountability log. Monitoring of drug accountability will be performed by monitors during site visits or remotely and at the completion of the trial.

At the conclusion of the study, and as appropriate during the course of the study, the investigator will return all unused study treatment, unused packaging and a copy of the completed drug accountability log to the Novartis monitor or to the Novartis address provided in the investigator folder at each site.

#### **5.5.3.2 Handling of additional treatment**

Not applicable.

## 5.5.4 Instructions for prescribing and taking study treatment

For the entire trial, regardless of randomization, the following rules apply:

- Ranibizumab should be administered in the study eye on the day of the study visit. In any case, study treatment has to occur within the visit window as described in [Section 6](#).
- Treatments of the fellow eye with ranibizumab must not be performed on the same day as treatments with ranibizumab of the study eye.
- When ranibizumab and laser photocoagulation are to be applied on the same day to the same eye, the laser treatment has to be applied at least 30 minutes before the ranibizumab injection. When ranibizumab and laser photocoagulation are not to be applied on the same day to the same eye, laser treatment can be deferred for up to 14 days relative to the ranibizumab treatment.
- Initially, Grid&Direct short pulse laser photocoagulation may be performed in a staged manner as macular hemorrhage and severe edema (thicker than 400 µm as a guide) resolve, i.e. initial laser treatment can be split into 2 or more sessions.
- On days when ranibizumab and/or laser treatment is to be administered, efficacy assessments and pre-injection safety measures (tonometry, slit lamp and fundus examinations) must be conducted before administration of ranibizumab and/or laser photocoagulation.

If study visit assessments and a corresponding treatment occur on separate days, a repeat ophthalmoscopy should be performed as safety check-up before treatment of the eye. Results will be documented in the source documents but not in the eCRF. If any concern arises, treatment needs to be cancelled and a re-evaluation needs to take place. Efficacy assessments (BCVA, ██████) already performed at the scheduled study visit should not be repeated on the day of treatment unless the patient indicates a sudden change in vision.

Instructions on how to prepare ranibizumab PFSs for intravitreal injection and its administration under aseptic conditions are provided in the package insert of the provided PFS. Information on pre- and post-injection procedures including administration of antibiotic eye drops is provided in [Appendix 2](#) and [Appendix 3](#), respectively. Laser photocoagulation should be applied as approved for the indication and further outlined below. Instructions on post-laser treatment procedures are outlined in [Appendix 4](#). Study treatment (ranibizumab, laser photocoagulation) prescribed and dispensed to the patient during the study must be recorded on the dosage administration record eCRF.

### 5.5.4.1 Treatment Period (Day 1 to Month 11)

#### Arm 1: Ranibizumab monotherapy

Patients will start study treatment with ranibizumab on Baseline (Day 1) and having reached stable status (i.e., satisfied stabilization criteria as per [Section 5.5.4.2](#)) ranibizumab treatment may be temporarily discontinued. Patients should be monitored monthly for VA and disease activity. Ranibizumab injections are given using PRN regimen i.e., according to the Japanese label of ranibizumab. The minimum gap required between 2 injections of ranibizumab will be  $30 \pm 7$  days.

If there is no improvement in VA [REDACTED] imaging over the course of the first 3 injections, continued treatment is not recommended and the patient may receive alternative treatment at the investigator's discretion (for consequences refer to [Section 5.6.2](#)).

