## Protocol summary

Protocol number	CRFB002EJP09
Title	A 12-month, phase IV, open-label, randomized, active controlled, 2-arm, multicenter study assessing the efficacy and safety of intravitreal Ranibizumab combined with Grid&Direct short pulse laser photocoagulation versus a PRN Ranibizumab monotherapy in Japanese patients with macular edema secondary to branch retinal vein occlusion (BRVO).
Brief title	Study to show a superior benefit in terms of reduction of ranibizumab injections in patients receiving ranibizumab plus laser photocoagulation combination therapy without loss of efficacy and safety.
Sponsor and Clinical Phase	Novartis Pharma K.K (Phase IV)
Investigation type	Drug, Laser photocoagulation
Study type	Interventional
Purpose and rationale	This study is designed to evaluate comparative efficacy and safety data as well as injection frequency data for ranibizumab using a pro re nata (PRN) dosing, administered with Grid&Direct short pulse laser photocoagulation versus ranibizumab monotherapy using the same dosing up to Month 12 in Japanese patients with visual impairment due to macular edema (ME) secondary to BRVO.
Primary Objective	To demonstrate that PRN regimen (PRN, according to the Japanese label of ranibizumab) of ranibizumab combined with Grid&Direct short pulse laser photocoagulation reduces the burden of frequent ranibizumab injections as compared to ranibizumab monotherapy. The primary objective will be assessed by the difference in the mean number of ranibizumab injections applied up to Month 11 between the 2 treatment arms.
Secondary Objectives	The secondary objectives of this study are as follows: 
 
• To evaluate the efficacy of each arm as assessed by Best-corrected visual acuity (BCVA)
 
• To evaluate the efficacy of each arm as assessed by center subfield thickness (CSFT)
 
• To evaluate the safety of ranibizumab monotherapy and ranibizumab combined with Grid&Direct short pulse laser photocoagulation therapy in Japanese patients as assessed by the type, frequency, and severity of ocular and non-ocular adverse events (AEs) from Baseline (Day 1) to Month 12
 

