## 1.2 Purpose

The present study will generate comparative efficacy and safety data as well as injection frequency data for 0.5 mg ranibizumab using a PRN dosing as defined in the protocol (i.e., according to the Japanese label of ranibizumab), administered with Grid&Direct short pulse laser photocoagulation versus 0.5 mg ranibizumab monotherapy using the same dosing (the current standard treatment) up to Month 12 in Japanese patients with visual impairment due to ME secondary to BRVO. [REDACTED]

[REDACTED] The results of this study will provide 1 year safety, efficacy and injection frequency data to further guide recommendations on the use of ranibizumab with or without laser photocoagulation in BRVO.

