## **Arm 2: Ranibizumab + Grid&Direct short pulse laser photocoagulation**

Patients will start study treatment with ranibizumab on Baseline (Day 1) and having reached stable status (i.e., satisfied stabilization criteria as per [Section 5.5.4.2](#)), ranibizumab treatment may be temporarily discontinued. Patients should be monitored monthly for VA and disease activity. Ranibizumab injections are given using PRN regimen i.e., according to the Japanese label of ranibizumab. The minimum gap required between 2 injections of ranibizumab will be  $30 \pm 7$  days.

Grid&Direct short pulse laser photocoagulation treatment must be applied to the target within vascular arcades as soon as indicated. If in the investigator's opinion dense macular hemorrhage and/or severe retinal edema preclude laser treatment, laser photocoagulation should be postponed until resolution of the hemorrhage permits laser treatment. The criteria for PRN of Grid&Direct short pulse laser photocoagulation is defined in [laser operation manual](#) in detail.

Following the complete application of the initial laser treatment, further laser treatment can be applied in the presence of ME due to BRVO at the investigator's discretion at minimal intervals of  $30 \pm 7$  days.

Laser photocoagulation will be optional if BCVA is greater than or equal to 0.8 in decimal VA which is equivalent to 0.12 units in logMAR (or 79 letters in ETDRS) or in the absence of ME.

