### **5.6.2 Discontinuation of study treatment**

Patients can discontinue treatment because of the appearance of a new health condition suspected to require appropriate care or require medications prohibited by the protocol ([Section 5.5.8](#)), unacceptable AEs, refusal to continue treatment, or at the investigator's discretion based on his/her clinical judgment.

Study treatment *must* be discontinued under the following circumstances:

- Emergence of the following AEs:
  - Rhegmatogenous retinal detachment
  - Stage 3 or 4 macular hole
  - Stroke or transient ischemic attack (TIA)
- Pregnancy
- Use of prohibited treatment as per [Table 5-1](#).
- Any other protocol deviation that results in a significant risk to the patient's safety.

The reason for study treatment discontinuation will be recorded on the Treatment Period Completion eCRF.

Patients who permanently discontinue study treatment and start certain prohibited treatments (see [Table 5-1](#)) should be withdrawn from the study and undergo all assessments for the Visit 14 (End of study (EOS)) as described in [Table 6-1](#).

Patients who discontinue study treatment and do not start a prohibited medication per [Table 5-1](#) should NOT be considered withdrawn from the study and continue their scheduled follow-up assessments until Visit 14 (EOS). A Study Treatment Period Completion eCRF should be completed, giving the date and primary reason for stopping study treatment.

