### **9.4.3 Handling of missing values/censoring/discontinuations**

No imputation is required for the primary endpoint which is number of ranibizumab injections, based on PRN regimen that is the number of injections during the study period will be used for the primary endpoint.

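### The advice against continuing ranibizumab after no improvement over the first 3 injections is written for Arm 1 only, so it can lower the control arm's injection count for a reason unrelated to laser

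*Protocol*

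**What the plan says.** Section 5.5.4.1 describes ranibizumab treatment separately for each arm. Start on Day 1, pausing once stable, monthly monitoring, PRN dosing under the Japanese label and the minimum gap between injections are worded the same way. The Arm 2 paragraph, for example, repeats that "ranibizumab treatment may be temporarily discontinued. Patients should be monitored monthly for VA and disease activity".

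The Arm 1 text then adds a sentence that Arm 2 lacks. Where there is no improvement "over the course of the first 3 injections, continued treatment is not recommended and the patient may receive alternative treatment", at the investigator's discretion. Part of the trigger is redacted, but not the arm it belongs to.

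None of the shared sections carries the advice over to Arm 2:

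- Section 5.5.4 has a list introduced by "For the entire trial, regardless of randomization, the following rules apply". The advice is not in it.
- Section 5.5.4.2 (re-treatment criteria) and section 5.5.5 (interruptions) do not mention it.
- Section 5.6.2 lets treatment stop in either arm at the investigator's "discretion based on his/her clinical judgment", without naming non-response. It also provides that "The reason for study treatment discontinuation will be recorded on the Treatment Period Completion eCRF".

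The primary analysis (section 9.4.2) uses observed data in the FAS. Section 9.4.3 adds no imputation: "the number of injections during the study period will be used for the primary endpoint".

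**The concern.** The prompt acts on the behaviour that the primary endpoint counts. An Arm 1 patient who is stopped on it stays in the FAS with a count of about 3. That reads as a low injection burden when it is a treatment failure. If the alternative treatment is one that Table 5-1 ties to leaving the study, the count ends there as well.

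Sections 3.2 and 5.4 make the trial open-label for the investigator. The person who decides whether to stop therefore knows the arm and has a written prompt in one arm only. The effect is to lower the control mean, and with it the saving that the trial is designed to show.

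The patients concerned may be ones who would otherwise have many injections. Under section 5.5.4.2, an eye whose central subfield thickness stays at 300 µm or more meets a re-treatment criterion at every visit. The schedule allows up to 12 injections (Day 1 plus Months 1 to 11). Section 1.1 gives poor responders and repeated recurrence as part of the reason for the study.

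**Working it through.** **1. The plan's own figure.** Section 9.8 assumes a difference of 2 injections, SD 2.32, one-sided alpha 0.025 and 80% power with a Wilcoxon-Mann-Whitney test. By Noether's formula, p = Φ(2 / (2.32 × √2)) = 0.729, and n per arm = (1.960 + 0.842)² / (6 × (0.729 − 0.5)²) = 24.96, so 25. With 10% drop-out, 25 / 0.9 = 27.8, so 28 per arm and 56 in total. The stated sample size reproduces and is not in dispute.

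**2. Effect of one stopped patient.** A patient held at 3 injections who would have had m lowers the Arm 1 mean of 28 patients by (m − 3) / 28. For m = 8 this is 5 / 28 = 0.18 injections, against the planned difference of 2.

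**3. Power.** The protocol gives neither arm means nor the share of non-responders, so both are assumed. The simulation drew beta-binomial counts on 1 to 12 with SD 2.32 and 28 per arm, without drop-out. It used a t-test at one-sided 0.025 and 40,000 replicates. A randomly chosen share q was capped at 3 injections, so stopped patients are typical of their arm. Means are 6 (Arm 1) v 4 (Arm 2). With no stopping, power is 0.880.

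| q in Arm 1 | Expected Arm 1 stops (28 × q) | Power, Arm 1 only | Power, Arm 2 at q/2 | Power, both at q |
|---|---|---|---|---|
| 2% | 0.6 | 0.855 | 0.860 | 0.865 |
| 5% | 1.4 | 0.820 | 0.836 | 0.853 |
| 10% | 2.8 | 0.741 | 0.789 | 0.820 |

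The cost of the asymmetry is the last column minus an earlier one:

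- No Arm 2 stops: about 1, 3 and 8 points. Repeat runs put the 10% case between 7 and 8.
- Arm 2 stopping half as often, through section 5.6.2: about 1, 2 and 3 to 4 points.

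**4. Estimated difference.** Arm 1 only v both arms gives 1.94 v 1.97, 1.85 v 1.92 and 1.69 v 1.84. The asymmetry therefore takes off 0.03, 0.07 and 0.15 injections.

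**5. Sensitivity, no Arm 2 stops, q = 2%, 5%, 10%.**

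- Means 7 v 5: cost 1.6, 4.7 and 10.8 points.
- Means 8 v 6: cost 1.8, 5.9 and 14.5 points.
- Means 6 v 4, stops only among patients above the median count: cost 3.0, 8.2 and 20.6 points. Another way of defining such stops gave about 2, 6 and 15.

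**6. Type I error.** With equal means (6 v 6) and stops in Arm 1 only, one-sided rejection is 0.019, 0.013 and 0.008 at q = 2%, 5% and 10%. All are below the nominal 0.025.

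**The case against.** The strongest reply is that the asymmetry may be deliberate. A non-responder on monotherapy has no other study treatment, whereas an Arm 2 patient can have further laser, so an exit route for Arm 1 alone is coherent. The protocol does not give this reason. It would explain offering alternative treatment in one arm, but not advising against further ranibizumab in one arm only, when ranibizumab is what is counted.

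The second reply is that the practical gap may be small. The wording is advisory, section 5.6.2 allows discretionary stops in either arm, and both arms follow the Japanese label. The label is not among the documents. If it carries the same advice, Arm 2 is already covered and only the wording needs correcting. This stands, and it limits how large the effect can be said to be.

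Third, every figure for size rests on assumptions, and the trigger is partly redacted. If it requires both visual and anatomical non-response, it could be rare. This also stands.

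Four stronger readings are tempting, and the documents do not support them:

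- **The text contradicts the stated common dosing.** The Protocol summary describes "ranibizumab monotherapy using the same dosing up to Month 12 in Japanese patients", and section 1.2 says much the same. Both describe the PRN regimen, which is the same in both arms. Advice on abandoning treatment is not clearly part of it.
- **Arm 1 patients must stop.** Nothing in the sentence is mandatory.
- **A positive result would be unsafe.** The bias runs against the laser arm.
- **The whole loss comes from the asymmetry.** At 10% stopping, power falls from 0.880 to 0.741, about 14 points. About 6 of these (0.880 to 0.820) would be lost with the same advice in both arms.

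**Conclusion.** The point holds as a modest design flaw, worth correcting but not decisive. One written prompt affecting the primary endpoint applies to the control arm only, in a trial where the treating investigator knows the arm. The consequence is a diluted estimate and some lost power. A significant saving would still stand, whereas a smaller or non-significant one could partly reflect control-arm stopping.

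The size cannot be fixed from the protocol. The central range of about 1 to 8 points assumes means of 6 v 4, SD 2.32, 28 per arm, 2% to 10% stopping in Arm 1, none in Arm 2, and stopped patients typical of their arm. The last assumption is probably favourable to the plan, given the re-treatment criteria. The assumption of no Arm 2 stops works the other way.

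**What to change.** Move the sentence from the Arm 1 paragraph of section 5.5.4.1 to the section 5.5.4 rules common to both arms, so that the advice on continuing ranibizumab is identical. Laser in Arm 2 continues under its own rules. Then report stops for non-response by arm, using the discontinuation reason already collected. The report is needed even after the change: if laser improves vision or oedema, fewer Arm 2 patients will meet the trigger, so equal wording does not ensure equal stopping.

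The cost is one relocated sentence and one disposition line, with no new data. The clinical price is that some Arm 2 patients may stop ranibizumab early. Section 11.1 requires a written amendment with ethics approval. Amendment 2 records 59 patients randomized by 21-Jan-2018 against a minimum of 56, so a late change reaches only patients not yet past their third injection. For the others, the report by arm is what remains.
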